5.7 Schematic diagram

The study schematic diagram for PS0008 is presented in [Figure 5–1](#).

Figure 5–1: Schematic diagram of PS0008

IGA=Investigator’s Global Assessment; IMP=investigational medicinal product; N=number; PASI=Psoriasis Area and Severity Index; Q4W=every 4 weeks; Q8W=every 8 weeks; SFU=Safety Follow-Up

Note: Refer to [Section 5.2.2](#) for treatments during the Initial Treatment Period and to [Section 5.2.3](#) for treatments during the Maintenance Treatment Period.

Note: At Week 28 and all following visits, subjects on continuous treatment with the same IMP for at least 12 weeks with a persistent IGA score ≥ 3 over at least a 4-week period are defined as nonresponders and should discontinue IMP.

5.8 Rationale for study design and selection of dose

5.8.1 Study design

A randomized, active-controlled study design has been selected to demonstrate efficacy and safety of bimekizumab for regulatory approval. The study population will include adults with moderate to severe chronic plaque PSO and allow subjects who have received previous biologic treatment as well as those who are biologic treatment naïve. The primary efficacy outcome measures (based on PASI and IGA) and other efficacy assessments included in this study are consistent with those used for other PSO studies and are considered appropriate for establishing efficacy of bimekizumab. An Initial Treatment Period of 16 weeks will be used to demonstrate the efficacy of bimekizumab compared with adalimumab. The study duration extends beyond the Initial Treatment Period (to 56 weeks) to allow for collection of long-term safety and efficacy data.

At Week 24, subjects on adalimumab treatment are re-allocated to treatment with bimekizumab 320mg Q4W. This allows for a controlled evaluation of the safety and efficacy of switching from a product with one mechanism of action to another, which is known to occur in clinical practice due to either loss of response or access. In a recent PSO study in which subjects were switched from adalimumab to a treatment with a different mechanism of action, there was no evidence of an increased safety risk following the switch without washout (Reich et al, 2017).

5.8.2 Dose selection

Bimekizumab doses ranging from 64mg to 480mg were evaluated in the Phase 2b multicenter, randomized, double-blind, placebo-controlled, parallel-group, dose-ranging study PS0010. Bimekizumab 320mg was found to have an acceptable safety profile, only required 2 injections per treatment administration, and achieved significant PASI responses at Week 12 (summarized in the IB). Furthermore, data from the Phase 2a multicenter, randomized, subject-blind, Investigator-blind study PS0016 and PK/PD modeling in this PSO population indicates improved responses through Week 16. Therefore, a bimekizumab dose of 320mg (Q4W initial and Q4W or Q8W maintenance) was selected for this study.

6 SELECTION AND WITHDRAWAL OF SUBJECTS

6.1 Inclusion criteria

To be eligible to participate in this study, all of the following criteria must be met at Screening and at the Baseline Visit:

1. Subject has provided informed consent.
2. Subject is considered reliable and capable of adhering to the protocol (eg, able to understand and complete diaries), visit schedule, or medication intake according to the judgment of the Investigator.
3. Male or female at least 18 years of age.
4. Chronic plaque PSO for at least 6 months prior to the Screening Visit.
5. PASI ≥ 12 and BSA affected by PSO $\geq 10\%$ and IGA score ≥ 3 on a 5-point scale.
- 6a. Subject is a candidate for systemic PSO therapy and/or phototherapy.

7. Subject must be considered, in the opinion of the Investigator, to be a suitable candidate for treatment with adalimumab per regional labeling and has no contraindications to receive adalimumab as per the local label.

8. Female subjects must be:

- Postmenopausal. Menopause is defined as 12 consecutive months of amenorrhea, for which there is no other obvious pathological or physiological cause.
- Permanently sterilized (eg, tubal occlusion, hysterectomy, bilateral salpingectomy).
- Or, if of childbearing potential (and engaged in sexual activity that could result in procreation), must be willing to use a highly effective method of contraception throughout the duration of the study until 20 weeks after last administration of IMP, and have a negative pregnancy test at Visit 1 (Screening) and immediately prior to first dose. The following methods are considered highly effective when used consistently and correctly:
 - Combined (estrogen and progestogen) hormonal contraception associated with inhibition of ovulation (oral, intravaginal, or transdermal)
 - Progestogen-only hormonal contraception associated with inhibition of ovulation (oral, injectable, implantable).
 - Intrauterine device.
 - Intrauterine hormone-releasing system
 - Vasectomised partner.
 - Abstinence as a form of birth control is generally not allowed in the study unless abstinence is in accordance with a subject's preferred and common lifestyle. Study personnel must confirm the continued use of abstinence is still in accordance with the subject's lifestyle at regular intervals during the study.

9. Subject agrees not to change their usual sun exposure during the course of the study and to use ultraviolet A/ultraviolet B sunscreens if unavoidable exposure occurs.

6.2 Exclusion criteria

Subjects are not permitted to enroll in the study if any of the following criteria are met:

1. Female subject who is breastfeeding, pregnant, or plans to become pregnant during the study or within 20 weeks following the final dose of IMP.
2. Subject has previously participated in a bimekizumab clinical study who received at least 1 dose of the IMP (including placebo).
- 3a Subject is currently participating in another study of a medication (systemic) under investigation. Subject must be washed out of the medication for 12 weeks or at least 5 half-lives prior to the Baseline Visit, whichever is greater.
- 4a. Subject is currently participating in another study of a topical medication under investigation. Subject must be washed out of the medication for 4 weeks prior to the Baseline Visit.

- 5a. Subject is currently, or was within the 4 weeks prior to the Baseline Visit, participating in another study of a medical device under investigation.
6. Subject has a known hypersensitivity to any excipients of bimekizumab or adalimumab.
7. Subject has a form of PSO other than chronic plaque-type (eg, pustular, erythrodermic and guttate PSO, or drug-induced PSO).
8. Subject has an active infection or history of infection(s) as follows:
 - Any active infection (except common cold) within 14 days prior to Baseline.
 - A serious infection, defined as requiring hospitalization or iv anti-infective(s) within 2 months prior to the Baseline Visit.
 - A history of opportunistic, recurrent or chronic infections that, in the opinion of the Investigator, might cause this study to be detrimental to the subject. Opportunistic infections are infections caused by uncommon pathogens (eg, pneumocystis jirovicii, cryptococcosis) or unusually severe infections caused by common pathogens (eg, cytomegalovirus, herpes zoster).
9. Subject has concurrent acute or chronic viral hepatitis B or C or human immunodeficiency virus (HIV) infection. Subjects who have evidence of, or tested positive for hepatitis B or hepatitis C are excluded. A positive test for the hepatitis B virus is defined as: 1) positive for hepatitis B surface antigen (HBsAg+) or 2) positive for anti-hepatitis B core antibody (HBcAb+). A positive test for the hepatitis C virus (HCV) is defined as: 1) positive for hepatitis C antibody (anti-HCV Ab) and 2) positive via a confirmatory test for HCV (for example, HCV polymerase chain reaction).
10. Subject has received any live (includes attenuated) vaccination within the 8 weeks prior to the Baseline visit (eg, inactivated influenza and pneumococcal vaccines are allowed but nasal influenza vaccination is not permitted).
11. Subject has received Bacillus Calmette-Guerin vaccinations within 1 year prior to the Baseline Visit.
12. Subject has known tuberculosis (TB) infection, is at high risk of acquiring TB infection, or has current or history of nontuberculous mycobacterium (NTMB) infection. A subject with LTB (a positive interferon-gamma release assay [IGRA] and diagnosis confirmed by TB specialist) may be rescreened once and enrolled after receiving at least 8 weeks of appropriate LTB infection therapy and if no evidence of therapy-related hepatotoxicity has occurred prior to the first injection (alanine aminotransferase [ALT]/aspartate aminotransferase [AST] remain ≤ 3 times upper limit of normal [ULN]).

Subject has a past history of active TB involving any organ system unless adequately treated according to World Health Organization/Centers for Disease Control (CDC) therapeutic guidance and proven to be fully recovered upon consult with a TB specialist.

Refer to [Section 12.3.1](#) for details on determining full TB exclusion criteria.
13. Subject has a history of a lymphoproliferative disorder including lymphoma or current signs and symptoms suggestive of lymphoproliferative disease.

- 14a. Subject has any active malignancy or history of malignancy within 5 years prior to the Screening Visit EXCEPT treated and considered cured cutaneous squamous or basal cell carcinoma, or in situ cervical cancer.
 15. Subject has a diagnosis of inflammatory conditions other than PSO or PsA, including but not limited to rheumatoid arthritis, sarcoidosis, or systemic lupus erythematosus. Subjects with a diagnosis of Crohn's disease or ulcerative colitis are allowed as long as they have no active symptomatic disease at Screening or Baseline.
 16. Subject has had major surgery (including joint surgery) within the 3 months prior to the Baseline Visit, or has planned major surgery within 6 months after entering the study.
 - 17a. Subject has any systemic disease (ie, cardiovascular, neurological, renal, liver, metabolic, gastrointestinal, hematological, immunological, etc.) considered by the Investigator to be uncontrolled, unstable, or likely to progress to a clinically significant degree during the course of the study.
 18. Subject has had myocardial infarction or stroke within the 6 months prior to the Screening Visit.
 19. Subject has laboratory abnormalities at Screening, including any of the following:
 - a. $\geq 3.0 \times$ ULN of any of the following: ALT, AST, alkaline phosphatase (ALP); or $> \text{ULN}$ total bilirubin ($\geq 1.5 \times \text{ULN}$ total bilirubin if known Gilbert's syndrome)
 - b. White blood cell (WBC) count $< 3.00 \times 10^3 / \mu\text{L}$
 - c. Absolute neutrophil count $< 1.5 \times 10^3 / \mu\text{L}$
 - d. Lymphocyte count < 500 cells/ μL
 - e. Hemoglobin $< 8.5 \text{ g/dL}$
 - f. Any other laboratory abnormality, which, in the opinion of the Investigator, will prevent the subject from completing the study or will interfere with the interpretation of the study results
- Individual screening tests for which the results are in error, borderline, or indeterminate for inclusion in the study can be repeated once for confirmation during the Screening Period. Upon retesting, subjects whose results remain outside this threshold should not be randomized.
20. Subject has any other condition, including medical or psychiatric, which, in the Investigator's judgment, would make the subject unsuitable for inclusion in the study.
 21. Subject has had previous exposure to adalimumab.
 22. Criterion deleted
 23. Subject has experienced primary failure (no response within 12 weeks) to 1 or more IL-17 biologic response modifier (eg, brodalumab, ixekizumab, secukinumab) OR more than 1 biologic response modifier other than an IL-17.
 24. Subject is taking PsA medications other than stable doses (ie, stable for at least 1 week prior to the Screening Visit) of nonsteroidal anti-inflammatory drugs (NSAIDs) or analgesics (see Section 7.8.1.2).

25. Subject has a history of chronic alcohol or drug abuse within 6 months prior to Screening as evaluated by the Investigator based on medical history, site interview, and/or results of the specified urine drug screen.
26. Presence of active suicidal ideation, or positive suicide behavior using the “Screening” version of the electronic Columbia Suicide Severity Rating Scale (eC-SSRS) and with either of the following criteria:
 - History of a suicide attempt within the 5 years prior to the Screening Visit. Subjects with a history of a suicide attempt more than 5 years ago should be evaluated by a mental healthcare practitioner (HCP) before enrolling into the study.
 - Suicidal ideation in the past month prior to the Screening Visit as indicated by a positive response (“Yes”) to either Question 4 or Question 5 of the “Screening” version of the eC-SSRS.
- 27a. Subject has presence of moderately severe major depression or severe major depression, indicated by a score of ≥ 15 using the screening PHQ-9. Medication used to treat depression should be stable for 8 weeks prior to Baseline.
28. Subject is a member of Investigator site personnel directly affiliated with this study and/or their immediate families. Immediate family is defined as a spouse, parent, child, or sibling, whether biological or legally adopted.
29. Subject is a UCB employee or employee of third-party organizations involved in the study.
30. Subject is taking or has taken prohibited psoriasis medications without meeting the mandatory washout period relative to the Baseline Visit (Table 7–2).

6.3 Withdrawal criteria

Subjects are free to withdraw from the study at any time, without prejudice to their continued care. Subjects who withdraw from the study should complete the PEOT Visit (see Section 8.4).

Subjects should be withdrawn from the study and will be encouraged to come back for the SFU visit 20 weeks after final dose of IMP if the subject withdraws his/her consent or the Sponsor or a regulatory agency requests withdrawal of the subject.

A subject should be withdrawn from IMP and will be asked to come back for the SFU visit 20 weeks after final dose of IMP if any of the following events occur:

1. Subject develops an illness that in the opinion of the Investigator would interfere with his/her continued participation if the risk of continuing IMP outweighs the potential benefit.
2. Subject develops erythrodermic, guttate, or pustular form of PSO.
3. Criterion deleted
4. Subject is noncompliant with the study procedures or medications in the opinion of the Investigator.
5. Subject uses prohibited concomitant medications, with the exception of topicals, as defined in this protocol (Section 7.8.2), that may present a risk to the safety of the subject or the integrity of the study data, in the opinion of the Investigator and/or the Medical Monitor.

6. Subject has a clinical laboratory value meeting any of the following criteria:
 - a. Hepatotoxicity as described in [Section 6.3.1](#)
 - b. A laboratory value meeting any of the following criteria:
 - Absolute neutrophil count $<1.0 \times 10^3/\mu\text{L}$
 - Absolute lymphocyte count $<0.2 \times 10^3/\mu\text{L}$

Subjects may remain in the study if the result is transient. A retest is required within 1 to 2 weeks at a scheduled or unscheduled visit. If the repeat absolute neutrophil count or absolute lymphocyte count is still below the allowable values, the subject must be withdrawn. If the repeat absolute neutrophil count or absolute lymphocyte count is above the allowable values, the subject may continue in the study.

7. The subject experiences a severe AE, an SAE, or a clinically significant change in a laboratory value that, in the opinion of the Investigator, merits the discontinuation of the IMP and appropriate measures being taken.
8. At Week 28 and all following visits, subjects on continuous treatment with the same IMP for at least 12 weeks with a persistent IGA score ≥ 3 over at least a 4-week period are defined as nonresponders and should discontinue IMP.
9. There is confirmation of a pregnancy during the study, as evidenced by a positive pregnancy test (see [Section 12.1.4](#) for more information regarding pregnancies).
10. A subject considered as having either a suspected new LTB infection or who develops active TB or NTMB infection during the study (including but not limited to, conversion demonstrated by IGRA or other diagnostic means) must be immediately discontinued from IMP and a PEOT Visit must be scheduled as soon as possible, but not later than the next regular visit.

The subject must be permanently withdrawn if further examinations result in a diagnosis of active TB, or if the subject is diagnosed with latent TB infection (LTBI) with no initiation of prophylactic treatment, prematurely discontinues prophylactic treatment, or, in the opinion of the Investigator or Sponsor, is noncompliant with prophylactic TB therapy.

Confirmed active TB is an SAE and must be captured on an SAE Report Form and provided to the Sponsor in accordance with SAE reporting requirements. As with all SAEs, periodic follow-up reports should be completed as per protocol requirements until such time as the TB infection resolves.

Additional information on TB policies is provided in [Section 12.3.1](#).

11. Subjects with newly diagnosed inflammatory bowel disease (IBD) or with IBD flares during the study must:
 - Be referred, as appropriate, to a health care professional treating IBD, such as a gastroenterologist
 - Discontinue IMP and be followed-up until resolution of active IBD symptoms

If IBD flares increase in severity or frequency during the study, the Investigator should use clinical judgement in deciding whether the subject should continue in the study and contact the

Medical Monitor and UCB study physician to confirm the subject's suitability for continued participation in the study.

12. Subjects **must be referred** immediately to a mental health care professional and may be withdrawn from the study based upon the Investigator's judgment of benefit/risk for:

- Active suicidal ideation as indicated by a positive response ("Yes") to Question 4 of the "Since Last Visit" version of the eC-SSRS.
- Moderately severe major depression as indicated by a PHQ-9 score of 15 to 19 if this represents an increase of 3 points compared to last visit.

13. Subjects must be referred immediately to a mental healthcare professional and must be withdrawn in case of:

- Active suicidal ideation as indicated by a positive response ("Yes") to Question 5 of the "Since Last Visit" version of the eC-SSRS
- Any suicidal behavior since last visit.
- Severe major depression as indicated by a PHQ-9 score ≥ 20 .

The mental health consultation must be recorded in source documentation.

Investigators should attempt to obtain information on subjects in the case of withdrawal or discontinuation. For subjects considered as lost to follow-up, the Investigator should make an effort (at least 1 phone call and 1 written message to the subject), and document his/her effort (date and summary of the phone call and copy of the written message in the source documents), to complete the final evaluation. All results of these evaluations and observations, together with a narrative description of the reason(s) for removing the subject, must be recorded in the source documents. The electronic Case Report Form (eCRF) must document the primary reason for withdrawal or discontinuation.

Investigators should contact the Medical Monitor, whenever possible, to discuss the withdrawal of a subject in advance.

6.3.1 Potential drug-induced liver injury IMP discontinuation criteria

Subjects with potential drug-induced liver injury (PDILI) must be assessed to determine if IMP must be discontinued. In addition, all concomitant medications and herbal supplements that are not medically necessary should also be discontinued.

The PDILI criteria below require immediate and permanent discontinuation of IMP for subjects with either of the following:

- ALT or AST $\geq 8xULN$
- ALT or AST $\geq 3xULN$ and coexisting total bilirubin $\geq 2xULN$

The PDILI criterion below requires immediate discontinuation of IMP for:

- Subjects with ALT or AST $\geq 3 \times \text{ULN}$ who exhibit temporally associated symptoms of hepatitis or hypersensitivity. Hepatitis symptoms include fatigue, nausea, vomiting, right upper quadrant pain or tenderness. Hypersensitivity symptoms include fever (without clear alternative cause), rash, or eosinophilia (ie, $>5\%$).

If a nondrug-related cause for the symptoms can be confirmed, these subjects may resume IMP administration after discussion with the responsible UCB physician, but only when the requirements for rechallenge with IMP as provided in [Section 12.2.1.2.1](#) are followed.

The PDILI criterion below allows for subjects to continue on IMP at the discretion of the Investigator.

- Subjects with ALT or AST $\geq 5 \times \text{ULN}$ and $< 8 \times \text{ULN}$, total bilirubin $< 2 \times \text{ULN}$, and no eosinophilia (ie, $\leq 5\%$), with no fever, rash, or symptoms of hepatitis (eg, fatigue, nausea, vomiting, right upper quadrant pain, or tenderness).

Evaluation of PDILI must be initiated as described in [Section 12.2.1](#) with repeat tests performed in 2 weeks. Upon re-test, if ALT or AST values have reduced to $< 5 \times \text{ULN}$, the subject can continue with the study. However, if ALT or AST remains $\geq 5 \times \text{ULN}$ and $< 8 \times \text{ULN}$ after re-test, IMP should be temporarily withheld and subject should undergo a repeat test in 2 weeks. If ALT or AST values remain $\geq 5 \times \text{ULN}$ even after the second re-test, then the subject should be permanently withdrawn from the study and should be followed for possible drug-induced liver injury.

If subjects are unable to comply with the applicable monitoring schedule, IMP must be discontinued immediately.

Investigators should attempt to obtain information on subjects in the case of IMP discontinuation to complete the final evaluation. Subjects with PDILI should not be withdrawn from the study until investigation and monitoring are complete. All results of these evaluations and observations, as well as the reason(s) for IMP discontinuation and subject withdrawal (if applicable), must be recorded in the source documents. The eCRF must document the primary reason for IMP discontinuation.

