≥5xULN (and ≥2x baseline) and <8xULN	<2xULN	No	
Discussion with Medical Monitor required.
 
Consider need for hepatology consult if there is no evidence of resolution (see Follow up requirements).^c
	
Further investigation – immediate IMP discontinuation not required (see Section 12.2.1.2).
 
IMP discontinuation required if any of the following occur:
 
 • Subject cannot comply with monitoring schedule. • Liver chemistry values continue to increase. • Liver chemistry values remain ≥5xULN (and ≥2x baseline) after 4 weeks of monitoring without evidence of resolution. 	
Essential: Every attempt must be made to have repeat liver chemistry values and additional testing completed within 48 hours at the site with HCP (see Section 12.2.1.3).
	
Monitoring of liver chemistry values at least twice per week for 2 weeks.^d
 
 • Immediate IMP discontinuation required if liver chemistry values continue to increase. 
After 2 weeks of monitoring liver chemistry values:
 
 • ALT or AST remains ≥5xULN <8xULN, IMP should be temporarily withheld and subject should undergo repeat test in 2 weeks. 
Continue IMP if ALT or AST values <5xULN; continue to monitor at least twice per week until values normalize, stabilize,

Table 12–3: Required investigations and follow-up for PDILI

Laboratory value			Immediate		Follow up	
ALT or AST	Total bilirubin	Symptoms ^a of hepatitis of hypersensitivity	Consultation requirements	Actions	Testing	Evaluation
						
or return to within baseline values.
 
If ALT or AST remains $\geq 5 \times \text{ULN}$ after second re-test, immediate, permanent IMP discontinuation required.
 
Continue to monitor until values normalize, stabilize, or return to within baseline values.^d

ALP=alkaline phosphatase; ALT=alanine aminotransferase; ASAP=as soon as possible; AST=aspartate aminotransferase; HCP=healthcare practitioner;

IMP=investigational medicinal product; NA=not applicable; PDILI=potential drug-induced liver injury; ULN=upper limit of normal

^a Hepatitis symptoms include fatigue, nausea, vomiting, and right upper quadrant pain or tenderness; hypersensitivity symptoms include eosinophilia (>5%), rash, and fever (without clear alternative cause).

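### The liver-injury rules conflict on two points: study withdrawal versus IMP stop at the second re-test, and whether a stop called permanent can be reversed

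*Protocol*

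**What the plan says.** **Second re-test.** Protocol Section 6.3.1 lets subjects with ALT or AST from 5 to below 8xULN, bilirubin below 2xULN and no symptoms stay on IMP at the Investigator's discretion, with a re-test at 2 weeks. If values are still in that range, IMP is withheld and a further test follows 2 weeks later. If they are still at or above 5xULN, "then the subject should be permanently withdrawn from the study and should be followed for possible drug-induced liver injury". For the same result the Evaluation column of Table 12-3 reads "after second re-test, immediate, permanent IMP discontinuation required", followed by continued monitoring.

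Section 6.3 keeps two kinds of withdrawal apart. Withdrawal from the study applies "if the subject withdraws his/her consent or the Sponsor or a regulatory agency requests withdrawal of the subject". A separate list opens "A subject should be withdrawn from IMP and will be asked to come back for the SFU visit", and its item 6a is "Hepatotoxicity as described in" Section 6.3.1. The last paragraph of 6.3.1 adds: "Subjects with PDILI should not be withdrawn from the study until investigation and monitoring are complete".

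**Rechallenge.** Section 6.3.1 makes the stop immediate and permanent for ALT or AST at or above 8xULN, and for ALT or AST at or above 3xULN with bilirubin at or above 2xULN. For symptomatic subjects at or above 3xULN the stop is immediate, and they may resume under Section 12.2.1.2.1 if a cause other than the drug is confirmed. Section 12.2.1, speaking of any stop made under 6.3.1, allows an exception where another diagnosis accounts fully for the liver findings and the 12.2.1.2.1 conditions are met.

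**The concern.** These are safety stopping rules, to be applied the same way at about 100 planned sites (Protocol Section 5.4). A site working from the body of 6.3.1 would take a subject off the study at week 4. A site working from Table 12-3 would stop IMP and keep the subject under liver monitoring. For a subject stopped at or above 8xULN, a site reading 6.3.1 would find no way back to IMP, whereas a site reading 12.2.1 would find one. At stake are consistent handling of liver events and complete follow-up of them.

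**Working it through.** The plan states no figure on this point, so the check sets the current passages side by side. The amendment log is not used.

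**1. Do the second re-test rules address the same moment?** Section 6.3.1: 2 weeks + 2 weeks = week 4. The Evaluation column of Table 12-3 uses the same two steps. The same subject with the same result therefore meets both rules at once:

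- Section 6.3.1, main text: permanent withdrawal from the study, with follow-up.
- Table 12-3, Evaluation: permanent IMP stop, with monitoring.
- Section 6.3, item 6a: hepatotoxicity listed as a reason to leave IMP.
- Section 6.3.1, last paragraph: no study withdrawal until investigation and monitoring are finished.
- Section 12.2.1.4: monitoring lasts until values normalize, stabilize or return to Baseline, so its end depends on the subject.

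One sequence fits all five: stop IMP at week 4, complete monitoring, then withdraw from the study. It requires the main-text sentence of 6.3.1 to mean a later step. That sentence ties withdrawal to the week 4 result and gives no later timing. Neither Table 12-3 nor item 6a mentions a later study withdrawal.

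**2. Who may be rechallenged?**

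- At or above 8xULN: permanent, no route back (6.3.1); rechallenge possible (12.2.1).
- At or above 3xULN with bilirubin at or above 2xULN: permanent, no route back (6.3.1); rechallenge possible (12.2.1).
- At or above 3xULN with symptoms: route back in both.

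Do the seven conditions in 12.2.1.2.1 shut out the first two groups? They include limits on ALT/AST and bilirubin, and absence of symptoms. If these described the original event, the symptom condition would bar the symptomatic group, which is the one group that 6.3.1 sends there. They must therefore describe the subject at the time of rechallenge. Read that way, they do not exclude the two groups called permanent. Conditions naming the original group: 0 of 7.

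**3. Does any passage settle it?** Section 12.2.1 opens by placing the discontinuation criteria in 6.3.1 and the follow-up in its own text. That points towards 6.3.1 but resolves neither conflict. The same section then qualifies the 6.3.1 stops, Table 12-3 carries stop rules of its own, and 12.2.1.2 cites 6.3.1 and Table 12-3 together.

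**4. Reach of the wording differences in Table 12-3.** The row's entry condition is "≥5xULN (and ≥2x baseline) and <8xULN", while 6.3.1 has no baseline multiple. A value at or above 5xULN is always at least twice a baseline of 5/2 = 2.5xULN or less. Exclusion criterion 19 removes ALT or AST at or above 3.0xULN at Screening. Assuming Baseline also stays below 3.0xULN, the multiple matters only for baselines above 2.5 and below 3.0xULN, and on-study values from 5 to below 2 x 3.0 = 6xULN.

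The Actions column has its own week 4 trigger: "Liver chemistry values remain ≥5xULN (and ≥2x baseline) after 4 weeks of monitoring without evidence of resolution". Example: baseline 2.8xULN, then 6.0, 5.5 and 5.3xULN at weeks 0, 2 and 4. At entry 6.0/2.8 = 2.14, so the row applies. At week 4, 2 x 2.8 = 5.6 exceeds 5.3, so this trigger is not met, while the Evaluation column's rule is. For baselines of 2.5xULN or less, the two columns differ only through the resolution qualifier, which is not defined.

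**The case against.** The best defence of the second re-test text is that 6.3.1 supplies its own order: its last paragraph postpones study withdrawal until monitoring is done, and its main text already requires follow-up. Section 8.4 narrows the gap further, since a subject withdrawn from the study is also withdrawn from IMP, has the Week 56 assessments and enters the Safety Follow-Up Period. The list heading in 6.3 is not conclusive either, because other items under it speak of leaving or remaining in the study. This stands in part: the passages can be followed in sequence. But the reader has to supply the sequence.

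On rechallenge, 12.2.1 can be read as a general rule with a stated exception. That is reasonable, but 6.3.1 gives no sign that its two permanent categories are subject to it, and it grants resumption expressly to one group only.

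A reader might infer two more contradictions, from the Table 12-3 columns and from the baseline multiple. The documents do not support that. The Actions column lists triggers any one of which is enough, and it never tells a site to continue or resume IMP when one is unmet. The Evaluation column therefore adds a trigger and opposes nothing. Where the baseline multiple is not met, the table row is silent while 6.3.1 still applies. Nor is it right to infer that nothing in the protocol bears on which text governs, because 12.2.1 does locate the discontinuation criteria in 6.3.1.

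**Conclusion.** Two conflicts in the current text hold: study withdrawal against IMP stop at the second re-test, and rechallenge after a stop that 6.3.1 calls permanent. Neither depends on the baseline value. The differences over the baseline multiple and evidence of resolution are untidy wording with little practical reach.

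It would go too far to say that the liver rules cannot all be followed. The second re-test passages can be followed if study withdrawal is taken as a later step, and the rechallenge passages if 12.2.1 is taken to qualify 6.3.1. The fault is that 6.3.1 says neither.

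The number of subjects affected cannot be estimated from the documents. Divergence in practice is limited: Section 12.2.1.1 requires the Medical Monitor to be notified within 24 hours and consulted, and rechallenge needs approval from the sponsor's physician, the DMC and a hepatologist. Little turns on this for the primary analysis, because a subject who stops IMP before Week 16 is a nonresponder whether or not they also leave the study (Protocol Section 14.3.1; SAP Section 4.2.1.1). The case for correction is patient safety and uniform conduct.

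**What to change.** Reconcile Section 6.3 item 6a, Sections 6.3.1, 12.2.1 and 12.2.1.2.1, and Table 12-3, so that each liver-injury group has:

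- one statement on whether the consequence is an IMP stop, study withdrawal or both, and when any study withdrawal falls relative to completing monitoring;
- one statement on whether rechallenge is open to that group.

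In the same edit, align the baseline-multiple and resolution qualifiers between the Table 12-3 columns and 6.3.1. Which clinical rule applies is for the sponsor to decide; this point asks only that the passages agree. The cost is a protocol wording clarification, with no added visits or tests.
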